5.2 Statistical Methods

Descriptive Statistics

Baseline values for demographic, clinical, and outcome will be tabulated for the study subjects. Continuous variables will be expressed as mean and standard deviation. Categorical variables will be expressed as percentages.

Analytical Statistics

The obtained shear wave measurements will be compared to MR elastography measurements to determine the AUC of EUS-SWE using MRE serving as the gold standard. Logistic regression will be used to generate ROC curves, and exploratory multivariable analyses using baseline differences in each group and other important clinical factors will be performed to identify confounders and interactions during the exploratory sensitivity analyses.

Handling of Missing Data

Subjects in which EUS shear wave measurements are unreliable (i.e., VsN < 70%) will not proceed to undergo MR elastography and will be excluded from the study, therefore will not be part of the statistical analysis. However, the subject will be recorded for the study to determine the rate of unreliable EUS shear wave measurements.

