Statistical Methodology	All continuous variables will be expressed as mean and standard deviation. Categorical variables will be expressed as percentages. Multivariate analysis will be performed.

1 Introduction

This document is a clinical research protocol relating to the prospective study on endoscopic ultrasound (EUS) shear wave elastography in assessment of liver fibrosis. The described study will be conducted in compliance with this protocol, applicable United States government regulations and Mayo Clinic policies and procedures.

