3.1 General Design

This is a prospective, paired study. Study subjects who are scheduled to undergo EUS at Mayo Clinic will be identified through Epic. Chart review will be performed including review of prior imaging, medical history, and laboratory results as available in Epic to determine study eligibility. Subjects without history of chronic liver disease (screened by low FIB-4 score) and those with known advanced fibrosis/cirrhosis will be eligible for the study. Eligible study subjects will then be contacted either before, or at the time of their endoscopy procedure to discuss study participation. All subjects will then receive standard clinical care based on the indication for the EUS procedure. During the EUS procedure, study subjects with undergo shear wave measurements obtained in a non-invasive manner as part of the endosonographic evaluation of the liver. 10 measurements (including shear wave velocity (Vs), elastic modulus (E)) will be obtained for point SWE (pSWE). Measurements will be obtained from both left and right lobes of liver unless technically infeasible to do so. Study subjects will then undergo a paired MR elastography (same day or at later date) after completion of EUS and only if consistent and reliable shear wave measurements were obtained (e.g., VsN > 70% (reliability index of each measurement expressed in percentages), IQR/M (interquartile range/ Median) is <15% for Vs and <30% for E). Enrolled study subjects who had undergone a previous MRE (within 6 months of enrollment) would be eligible for the study, without the need to undergo further research MRE. After completion of MR elastography, the subjects will then continue through their routine clinical care and will not be followed up by research staff. The expected duration of subject participation is anticipated to begin at the time of study enrollment and terminate after completion of MR elastography. There will be no additional follow up.

3.2

Figure 1: Study Design

[figure not shown]

Table 1: Schedule of Events (SOE)

	Baseline Screening & Enrollment Visit 1 Days -180 to 0	Accrual: Study Intervention Visit 2 Day 0	Follow up Visit 3 Days 0 to 60
Inclusion/Exclusion	X		
EUS and Shear wave Elastography		X	
MRE	X*		X*

**MRE only required to be conducted once. Patients undergoing MRE for clinical purposes within the study timeframe can be recruited using the clinically performed MRE result.*

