4.1 Inclusion Criteria

1. Adults over 18 years of age who are undergoing EUS procedures.
2. Subjects with history of chronic liver disease, advanced fibrosis, or cirrhosis.
3. Subjects without any history of chronic liver disease.
4. Subjects able to give appropriate consent to the study.

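### Section 5.2 picks covariates for its exploratory models from baseline group differences, with no cap or optimism correction at 50 or fewer subjects, so any multivariable AUC reported would be optimistic

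*Combined protocol and SAP*

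**What the plan says.** Section 5.2 (Statistical Methods) sets the main analysis as a comparison of shear wave and MRE measurements "to determine the AUC of EUS-SWE using MRE serving as the gold standard". No covariate appears there. The next sentence has logistic regression produce the ROC curves and adds that "exploratory multivariable analyses using baseline differences in each group and other important clinical factors will be performed to identify confounders and interactions", as part of sensitivity analyses that it again calls exploratory. The plan has no covariate list, limit on number, entry threshold or internal validation. It does not say whether an AUC from a multivariable model will be reported.

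On how the groups are formed, section 3.1 (General Design) says: "Subjects without history of chronic liver disease (screened by low FIB-4 score) and those with known advanced fibrosis/cirrhosis will be eligible for the study". No FIB-4 cutoff is given. Section 4.1 (Inclusion Criteria) lists the controls only as "Subjects without any history of chronic liver disease". FIB-4 is nowhere named as a covariate, and nowhere ruled out as one.

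The Study Summary says only "Multivariate analysis will be performed", without the word exploratory.

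**The concern.** The selection rule does not suit its stated aim. For a variable to confound the accuracy of EUS-SWE, it must shift the shear wave reading among subjects of the same disease status as well as differ between the groups. A baseline difference shows only the second of these. For an interaction, where accuracy varies with a patient factor, a group difference is neither necessary nor sufficient.

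In this design many baseline differences come from how subjects were chosen or from the disease itself. Controls are screened by low FIB-4 and cases have known advanced fibrosis or cirrhosis, so FIB-4 and its inputs are likely to differ and to qualify. A model that includes them scores how well the groups were separated at recruitment, and says little about what EUS-SWE contributes.

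The second problem is sample size. With at most 50 subjects, and fewer after unreliable measurements are removed, a data-chosen set of covariates and interactions fits noise. A multivariable AUC printed beside the primary one could be read as the performance of EUS-SWE. Section 5.1 plans on 0.89 for EUS-SWE and 0.972 for MRE, so even moderate optimism could change how the comparison looks.

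**Working it through.** **Inputs from the documents.** Enrolment is 50 (section 4). The planning AUC is 0.89 for EUS-SWE and 0.972 for MRE (section 5.1). The power figures in section 5.1 play no part in this point.

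**Assumptions, not in the documents.** The case/control split (25/25 or 10/40), the number and nature of the covariates, FIB-4's accuracy and cutoff, and independence of FIB-4 and EUS-SWE within groups.

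**Step 1: set-up.** EUS-SWE is taken as N(0,1) in controls and N(d,1) in cases. AUC = Φ(d/√2), so d = √2 × Φ⁻¹(0.89) = 1.414 × 1.2265 = 1.735.

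**Step 2: EUS-SWE alone.** A logistic model with one predictor keeps the rank order of the measurement, so its AUC is that of the measurement. Simulation at 25/25 agrees: mean apparent AUC 0.892, new-data AUC 0.890. The Hanley-McNeil standard error uses Q1 = 0.89/1.11 = 0.802 and Q2 = 2 × 0.89²/1.89 = 0.838:

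variance = [0.89 × 0.11 + 24(0.8018 − 0.7921) + 24(0.8382 − 0.7921)] / 625 ≈ 0.0023, SE ≈ 0.048, 95% CI about 0.80 to 0.98.

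**Step 3: add pure-noise covariates** (600 simulated studies per scenario). Apparent AUC is computed in the fitted data; new-data AUC applies the same score to fresh subjects.

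| Split | Noise covariates | Apparent | New data | Gap |
|---|---|---|---|---|
| 25/25 | 3 | 0.905 | 0.872 | 0.033 |
| 25/25 | 5 | 0.919 | 0.858 | 0.061 |
| 25/25 | 8 | 0.936 | 0.836 | 0.100 |
| 10/40 | 3 | 0.913 | 0.863 | 0.050 |
| 10/40 | 5 | 0.931 | 0.842 | 0.089 |
| 10/40 | 8 | 0.955 | 0.809 | 0.146 |

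At 10/40 with 8 covariates, 28% of runs showed complete separation.

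Results when covariates are chosen from 10 noise candidates depend on the rule. Keeping those with p<0.05 gives 0.902 to 0.907 apparent against 0.871 to 0.877 in new data. Keeping the five that differ most between groups, at 25/25, gives 0.929 against 0.845, a gap of 0.084.

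**Step 4: add a FIB-4-like score** (400 simulated studies). Assume that it has an AUC of 0.75 to 0.85 before selection and that controls are limited to its lowest 50% to 70%. Selection alone lifts the score's own AUC to 0.88 to 0.98. EUS-SWE plus the score reaches 0.96 to 0.99, while EUS-SWE alone stays at about 0.89.

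**Step 5: scale.** The planning difference between the tests is 0.972 − 0.89 = 0.082. With five noise covariates at 25/25 the apparent AUC exceeds the true value by 0.919 − 0.89 = 0.029, and with eight by 0.936 − 0.89 = 0.046. Both are below one standard error (0.048). The range in step 4 includes the MRE planning value.

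**The case against.** The strongest reply is that the main result is untouched. Section 5.2 defines the AUC of EUS-SWE against MRE without covariates, and step 2 shows that a one-predictor logistic model leaves it unchanged. The covariates belong to analyses called exploratory twice in the same sentence. This stands, and it is why the severity is low.

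A reader might infer three stronger things that the documents do not support.

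- **That covariates enter the ROC model behind the primary AUC.** ROC generation and multivariable work share a sentence, but nothing says so. The natural reading is that they are separate.
- **That FIB-4 will be a covariate.** This follows only from applying the rule to the design. The phrase about other clinical factors leaves discretion, and the groups being compared are not defined in that sentence.
- **That a multivariable AUC would be near perfect whatever EUS-SWE adds.** One set of simulations gives 0.981 to 0.998 with complete separation in 14% to 78% of studies. It assumes that a FIB-4-like score enters, with controls cut at 0 to 0.5 SD and cases shifted by 1 to 2 SD. Without such a variable the optimism is moderate.

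Two further replies also stand. The missing word exploratory in the Study Summary is the brevity of a synopsis and does not contradict section 5.2. And whether low-FIB-4 controls set against known cirrhosis inflate the EUS-SWE AUC itself is a separate question about case mix, which lends no weight here.

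What the reply does not answer is the rule itself. Calling an analysis exploratory does not make group differences a sound way to find confounders or interactions, and it does not correct an optimistic AUC.

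**Conclusion.** The point holds for the exploratory multivariable analyses only. Choosing covariates by baseline group difference favours variables that formed the groups or follow from the disease over factors that alter test accuracy, and the plan puts no limit on their number.

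If a multivariable AUC is reported, the gap between apparent and new-data AUC is about 0.03 to 0.10 with 3 to 8 noise covariates at 25/25, and about 0.05 to 0.15 at 10/40. If FIB-4 is entered, an apparent AUC of about 0.96 to 0.99 is plausible under the assumed FIB-4 accuracy and cutoff. The split, the covariate count and the FIB-4 behaviour are all assumptions. The planning AUC of 0.89 is the sponsor's. The primary EUS-SWE AUC is not affected when EUS-SWE is the only predictor. This is a cheap improvement of low severity.

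**What to change.** In section 5.2:

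1. State that the primary AUC uses EUS-SWE as the only predictor.
2. Replace selection by group differences with one or two prespecified factors that could modify accuracy. BMI is the obvious candidate, since section 1.4.1 gives it as a reason for the technique. Examine each as an exploratory interaction or covariate-specific ROC, with its confidence interval.
3. Keep FIB-4, its inputs and any other group-forming variable out of every model whose AUC is reported.
4. Report any multivariable AUC together with a bootstrap optimism-corrected value, repeating any covariate selection within each bootstrap sample.

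The cost is a few sentences and a bootstrap on data already collected. Exploratory AUCs will look less favourable, and the modifier estimates will be imprecise: in a stratum of 25 split 12/13, the Hanley-McNeil SE at 0.89 is about 0.07, so a 95% interval of about ±0.14. That imprecision should be shown.

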5.3 Subject Population(s) for Analysis

Subjects who have completed both EUS shear wave elastography and MR elastography will be included in the analysis.

6 Safety and Adverse Events

The EUS Shear wave elastography is being performed clinically and the safety and adverse events are not different from those inherent to the EUS procedure. Shear wave measurements typically require 5-10 minutes of procedural time.

There are no expected clinical adverse events for the study as the study intervention (MRE) is a non-invasive scan without any published safety concerns. Therefore, this study will not track any adverse events.

Definitions

Adverse Effect (Event)

Any untoward medical occurrence in a subject involved in clinical study of an investigational device; regardless of the causal relationship of the problem with the device or, if applicable, other study related treatment(s).

Revised 6/1/2021

Life-threatening adverse effect: Any adverse effect that places the subject, in the view of either the investigator or the sponsor, at immediate risk of death from the effect **as it occurred**. It does not include a reaction that, had it occurred in a more severe form, might have caused death.

Serious adverse effect: An adverse effect is considered “serious” if, in the view of either the investigator or the sponsor, it results in any of the following outcomes:

- death
- a life-threatening AE
- inpatient hospitalization or prolongation of existing hospitalization
- a persistent or significant disability/incapacity
- a congenital anomaly/birth defect.

Unanticipated adverse effect: Any adverse effect, the nature, specificity, severity, or frequency of which is not consistent with the risk information in the clinical study protocol or elsewhere in the current IDE application.

All inclusion and exclusion criteria are set out and there will be no protocol deviation.

7 Data Handling and Record Keeping

7.1 Confidentiality

Information about study subjects will be kept confidential and managed according to the requirements of the Health Insurance Portability and Accountability Act of 1996 (HIPAA). Those regulations require a signed subject authorization informing the subject of the following:

- What protected health information (PHI) will be collected from subjects in this study?
- Who will have access to that information and why?
- Who will use or disclose that information?
- The rights of a research subject to revoke their authorization for use of their PHI.

In the event that a subject revokes authorization to collect or use PHI, the investigator, by regulation, retains the ability to use all information collected prior to the revocation of subject authorization. For subjects that have revoked authorization to collect or use PHI, attempts should be made to obtain permission to collect at least vital status (long term survival status that the subject is alive) at the end of their scheduled study period.

7.2 Source Documents

Source data comprise all information, original records of clinical findings, observations, or other activities in a clinical trial necessary for the reconstruction and evaluation of the trial. Source data are contained in source documents. Examples of these original documents, and data records include: hospital records, clinical and office charts, laboratory notes, memoranda, subjects' diaries or evaluation checklists, pharmacy dispensing records, recorded data from automated instruments, copies or transcriptions certified after verification

Revised 6/1/2021

as being accurate and complete, microfiches, photographic negatives, microfilm or magnetic media, x-rays, subject files, and records kept at the pharmacy, at the laboratories, and at medico-technical departments involved in the clinical trial. When applicable, information recorded on the CRF shall match the Source Data recorded on the Source Documents.

Data Management

All data points gathered for the study will remain confidential and only available to designated research personnel. The data will be managed using Excel Subject Tracking.

Data Security and Confidentiality

All collected data points and information will be securely stored in Mayo Clinic issued laptops, desktops or tablets with password encryption. Only study personnel will have access to the study data and information.

7.3 Records Retention

The study team will maintain records and essential documents related to the conduct of the study. These will include subject case histories and regulatory documents.

The study team will retain the specified records and reports during the study and for the longer of the following.

1. As outlined in the Mayo Clinic Research Policy Manual –“Retention of and Access to Research Data Policy”

OR

2. A period of 2 years after the latter of the following two dates: The date on which the investigation is terminated or completed, or the date that the records are no longer required for purposes of supporting a premarket approval application or a notice of completion of a product development protocol.

8 Study Monitoring, Auditing, and Inspecting

8.1 Study Monitoring Plan

The investigator will allocate adequate time for such monitoring activities. Data safety monitoring plan (DSMP) will be completed after the first subject, then at 3 months and then annually if required. Delegated study staff will conduct the review. The review will be written up as reports and submitted to IRB for further review if required. The Investigator will also ensure that the monitor or other compliance or quality assurance reviewer is given

Revised 6/1/2021

access to all the study-related documents and study related facilities (e.g., pharmacy, diagnostic laboratory, etc.), and has adequate space to conduct the monitoring visit.

8.2 Auditing and Inspecting

The sponsor-investigator will permit study-related monitoring, audits, and inspections by the IRB, the monitor, and government regulatory agencies, of all study related documents (e.g., source documents, regulatory documents, data collection instruments, study data etc.). The sponsor-investigator will ensure the capability for inspections of applicable study-related facilities (e.g., pharmacy, diagnostic laboratory, etc.).

9 Ethical Considerations

This study is to be conducted according to United States government regulations and Institutional research policies and procedures.

This protocol and any amendments will be submitted to a properly constituted local Institutional Review Board (IRB), in agreement with local legal prescriptions, for formal approval of the study. The decision of the IRB concerning the conduct of the study will be made in writing to the sponsor-investigator before commencement of this study.

All subjects for this study will be provided a consent form describing this study and providing sufficient information for subjects to make an informed decision about their participation in this study. This consent form will be submitted with the protocol for review and approval by the IRB for the study. The formal consent of a subject, using the Approved IRB consent form, must be obtained before that subject undergoes any study procedure. The consent form must be signed and dated by the subject or the subject's legally authorized representative, and the individual obtaining the informed consent.

10 Study Finances

10.1 Funding Source

This is an investigator-initiated and investigator-funded study.

11 Publication Plan

The results of the study will be written up and submitted to gastroenterology/endoscopy/hepatology journals for publication.

12 References

There is minimal available literature on this topic. We are performing a small pilot study with retrospective then prospectively collected EUS shear wave measurements. The preliminary results suggest that EUS shear wave carries good diagnostic accuracy in differentiating subjects with normal liver stiffness and those with advanced fibrosis/cirrhosis. The results will require full statistical analyses. However, our positive observation with the pilot study will form the basis of our current comparative study between EUS shear wave and MRE.
